During large measles outbreaks, WHO recommends using an MCV starting at 6 months to prevent measles among young infants. This dose of MCV should be considered only as MCV 0 dose and parents are advised to bring their infants to receive a routine MCV first dose at 9 months. Most studies of immunogenicity of measles containing vaccine in infants <9 months were conducted using a measles single antigen vaccine. There is a limited data on immunogenicity of MR vaccine administered at < 9 months of age and its impact on immunogenicity of MR vaccine routinely administered at 9 months. As more countries are introducing MR vaccine in their routine immunization program (at 9 months) we propose a study that will assess the immunogenicity of MR vaccine at 6 months (MCV 0 dose) and its impact on immunogenicity of MR vaccine administered at 9 months (MCV1 dose).

Relevance:

The primary purpose of the study is to assess the immunogenicity of MR vaccine when delivered at 6 months. In addition, the study will establish the equality of MR vaccine seroconversion administered at 9 months following administration of an earlier MR vaccine dose at 6 months of age compared to MR vaccine dose administered at 9 months without previous MR vaccination. This study will also provide additional data on safety and tolerance of MR vaccine given at 6 months, and impact of maternal antibodies on immunogenicity of MR vaccine at 6 months.

Hypothesis:

Our study hypothesis is that the proportion of children seroconverting after administration of MR vaccine dose at 9 months, and who had received an MR vaccine dose at 6 months of age, is not different from that obtained after administration of MR vaccine dose at 9 months in infants who had no previous dose of MR vaccine.

Primary objectives:

1. To assess immunogenicity of MR vaccine at 6 months of age
2. To assess immunogenicity of MR vaccine at 9 months of age among children without prior measles and rubella vaccination, compared with MR vaccine immunogenicity among those who had a prior MR vaccination at 6 months of age

Secondary objectives:

1. To assess the frequency of adverse reactions following administration of MR vaccine at 6 months
2. To compare the immunogenicity of the MR vaccine first dose administered at 6 months vs at 9 months.
3. To assess the proportion of mothers with undetectable, detectable and protective levels of measles and rubella antibodies

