4. To determine the extent of variation in measles antibodies in women of child bearing age in a population with a long standing measles vaccination program
5. To determine the extent of variation in rubella antibodies in women of child bearing age in a population where rubella vaccine have been recently introduced
6. To determine if variation in antibody levels in infants at 6 months is predominately explained by variation in starting antibody levels in the mother in this population
7. To estimate the half-life of decay of measles and rubella antibodies in infants

Methods:

This study will be an open-label, randomized, 2-arm clinical trial in healthy infants in Bangladesh. 620 children will be enrolled and randomized at 6 months of age to one of two study arms. The study design and participant evaluations are illustrated in Table.

Table: Schematic representation of study arms

Arm		Age of participant				
		6 months	9 months	11 months	Sample size	Enrollment target (sample size + 10% attrition)
A	MR 6 & 9 months	MR •	MR •	•	279	310
B	MR 9 months	•	MR •	•	279	310
Total (infants)					558	620
	Mothers	•			558	620

• Indicates blood collection
MR- Measles -rubella vaccination

Outcome measures/variables:

The primary end-point assessment will be based on **measles antibody titers (mIU/ml) (measured by the multiplex bead assay (MBA))** and rubella titers (IU/mL) (measured by ELISA) on sera collected 8 weeks after completion of vaccination series (at 11 months of age). Immune response is defined at 8 weeks after completion of vaccination series, as seropositivity post-vaccination if pre-vaccination antibody was undetectable (i.e. seroconversion), or a 4-fold or greater increase in antibody titers among pre-vaccination seropositives after adjusting for decline in maternal antibodies. Seroprotection is defined as antibody level of ≥ 120 mIU/mL for measles and >10 IU/mL for rubella. We will calculate the proportion of children attaining post-vaccination protective levels of antibodies.

Description of the Research Project

Hypothesis to be tested

Does this research proposal involve testing of hypothesis: No Yes (describe below)

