1. The study physician will complete the study questionnaire and examine the participant
2. 1 ml of blood will be drawn from each infant (both study arms A and B).
3. Study vaccine will be administered to ALL infants (both study arm A and B). The participant will be observed for 30 minutes to monitor for any adverse reactions
4. Schedule the next visit at 11 months of age

MR vaccination at 9 months is now routinely given in Bangladesh. Therefore, there will be no follow-up household safety monitoring visit after the 9 month MR dose during the study.

Temporary exclusion

- Participants who meet temporary exclusion criteria for vaccination will be excused for the day and will be requested to return several days later, but as long as their age is 9 months, +/- 7 days. A note will be made in the study log book.

Study site visit at 11 months of age. Blood draw and Study exit.

This visit will be the third and last planned study visit for participants. During this visit, the following procedures will be conducted:

1. The study physician will complete the follow up form and examine the participant
2. 1 ml of blood will be drawn from each infant (from both study arms A and B).
3. At study exit, parents will be reminded to bring their child to the fixed site clinic or another EPI facility to receive their second dose of measles vaccine according to the new EPI schedule (at age 15 months).

Laboratory evaluations

Clinical Laboratory Evaluations

No clinical laboratory evaluations will be offered in this study. Laboratory assays described in the protocol are for research purposes only and laboratory results will not be used for clinical diagnosis.

Special Assays or Procedures

Blood samples will be obtained at 6 months from all infants (at enrolment) and mothers and tested for measles and rubella antibodies. The baseline levels will identify infants who have transplacentally transferred maternal antibodies been exposed to natural measles infection before the enrolment to the study. The mothers' antibody levels will be determined and they will be classified as "susceptible" or "protected" (seroprotection definitions will be the same: titer of ≥ 120 mIU/mL for measles and rubella >10 mIU/mL).

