For participants in the study group A, the immune response to the 6 month MR dose will be measured at 9 months (blood drawn during the second visit) to evaluate both the proportion seroconverting (from negative to protected), 4-fold or greater increase in antibody titers among pre-vaccination seropositives, after adjusting for decline in maternal antibodies, as well as the magnitude of the immune response (expressed as geometric mean titers of the antibody response). The rate of decay of maternal measles and rubella antibodies will be calculated in infants in arm B based on the difference of antibody levels measured at 6 months (baseline) and 9 months. We will incorporate the model of maternal measles and rubella decay for infants in arm A to measure post-vaccine antibody levels and impact of the maternal

antibody to immune response in infants who had measles or rubella antibodies at enrolment. In the recently published study from Bangladesh, baseline measles virus serum neutralizing antibody seroprotection and anti-rubella virus IgG seroprotection at 9 months of age was low (0.42-1.25% and 0-0.42%, respectively) (21). If during this study, we determine that most children have no detectable levels of maternal measles or rubella antibodies at 6 months it would be impossible to calculate the decay. In this case, we will refer to antibody decay rates reported elsewhere (29, 30).

THE FOLLOWING CHANGES ARE MADE TO THE PROTOCOL:

Since the inception of the project and completion of the field data collection a newer assay, multiplex bead assay (MBA) for measles and rubella has been developed. It has been validated by the CDC measles and rubella laboratories.

Multiplex Bead Assay (MBA) for Serum Antibody Detection of Measles and Rubella

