Multiplex bead assay detects antibodies against viral proteins in the serum of individuals who have been exposed to measles or rubella either by vaccination or natural infection. The MBA works by reading the fluorescent intensity of antigen-specific antibodies in serum binding to antigen coated beads and converting to antibody concentration using a standard curve. This is a novel IgG test for measles and rubella used at research labs. It is not commercially available and requires a significant amount of preparatory work to run the test and is not yet used to diagnose or confirm recent infection (IgM). Developing this capacity is not required for routine measles and rubella surveillance which the Bangladesh National Lab performs. Moreover, icddr,b has no prior experience in running MBA tests.

Measles and Rubella MBA testing will be conducted by the Measles, Mumps, Rubella, and Herpesvirus Laboratory at CDC, a WHO reference laboratory for measles virus. These tests will be performed as described by Smits et al.(31) The analytical cut-off value in the measles MBA assay is 153 mIU/ml. The concentration of antibody \geq 153 mIU/ml will be considered to be protective for measles. The analytical cut-off value in the rubella MBA assay is 9.36 IU/ml. The concentration of antibody \geq 9.36 IU/ml will be considered to be protective for rubella. There may be a formal comparison of rubella IgG concentrations between MBA and the standard EIA results.

Following testing of the samples by MBA, 5%-10% of the samples will also be tested by PRN for quality control testing.

Additional information regarding this assay is included in a detailed protocol maintained at the study laboratory.

Serum Measles IgG Antibody Detected by ELISA

Measles IgG testing will also be conducted by the Measles, Mumps, Rubella, and Herpesvirus Laboratory at CDC.

A commercial enzyme-linked immunosorbent assay (ELISA) will be used for the qualitative detection of IgG antibodies to Measles virus in human serum (Zeus Scientific Inc). Antigen specific antibody in the serum specimen binds to immobilized antigen and is complexed with an antibody linked to an enzyme. The color intensity of the solution depends upon the antibody concentration in the original test sample.

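### Measles endpoints are read on the bead assay, whose stated protective level is 153 mIU/mL, but seroprotection, baseline and maternal classes still use 120, the neutralisation-test limit

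*Combined protocol and SAP*

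**What the plan says.** **Assay.** The Project Summary (Outcome measures/variables), the endpoint text that follows the sample size section, and the main Outcome measures/variables section all read measles on MBA. MBA was brought in by a change described under Special Assays or Procedures: "Since the inception of the project and completion of the field data collection a newer assay" was developed.

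**MBA limit.** The MBA section states "The analytical cut-off value in the measles MBA assay is 153 mIU/ml", and that a concentration at or above "153 mIU/ml will be considered to be protective for measles". One number is both the analytical cut-off and the protective level.

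**Definitions still at 120.** The Project Summary says "Seroprotection is defined as antibody level of ≥ 120 mIU/mL for measles and >10 IU/mL for rubella". The main Outcome measures/variables section and General analytical issues repeat 120 for measles. Special Assays or Procedures classes the mothers by the same definition, "titer of ≥ 120 mIU/mL for measles and rubella >10 mIU/mL". Primary analytical approach labels baseline seropositives at 1:120 mIU/mL, which mixes a dilution with a concentration.

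**Where 120 comes from.** The PRNT section gives it as the interpretive cut-off of the neutralisation test and defines seroconversion as crossing 120 in neutralising antibody. That test is now quality control for MBA on 5-10% of samples.

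**Response wording.** The Project Summary defines the response "as seropositivity post-vaccination if pre-vaccination antibody was undetectable (i.e. seroconversion"), or a 4-fold rise among pre-vaccination seropositives. Special Assays or Procedures describes "the proportion seroconverting (from negative to protected"). Secondary objective 3 is "To assess the proportion of mothers with undetectable, detectable and protective levels of measles and rubella antibodies".

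**The concern.** A decision threshold should class a given result one way. Here the assay name was updated in the outcome sections but the number was not, so the Project Summary and the main Outcome measures/variables section each name MBA and then state 120. An analyst who follows the data analysis text would use 120; one who follows the assay section would use 153. No section says which takes precedence.

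Every reported measles seroprotection proportion, and the mothers' class, depends directly on this choice. The primary response is touched less directly: the cut-off decides who counts as negative before vaccination and positive after it, and the only numeric measles seroconversion rule is written for neutralising antibody. Two further gaps follow. The Project Summary requires pre-vaccination antibody to be undetectable, with no MBA meaning given. Secondary objective 3 needs three maternal classes, but the protocol states only one measles MBA limit.

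**Working it through.** **1. The sections side by side, for an MBA measles result from 120 to below 153 mIU/mL**

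| Section | Limit | Class |
|---|---|---|
| Multiplex Bead Assay | ≥153 | not protected |
| Project Summary, Outcome measures/variables | ≥120 | protected |
| Special Assays or Procedures (mothers) | ≥120 | protected |
| Main Outcome measures/variables | ≥120 | protected |
| General analytical issues | ≥120 | protected |
| Primary analytical approach (baseline label) | 1:120 as printed | seropositive |
| PRNT section | ≥120 | applies to neutralisation results only |

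The conflict is direct for seroprotection and for the mothers. The baseline label changes nobody's inclusion, because these children are kept in the analysis either way.

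**2. The plan's own figures.** The cut-offs are stated values, so there is nothing to reproduce. The sample sizes do not involve a cut-off. The 279 per arm reproduces from 75% v 65% at 80% power with one-sided alpha 0.05 and a continuity correction, and 279/0.9 = 310. The 271 reproduces as 1.645² × 0.25/0.05² = 270.6. The planning rates are not tied to an MBA limit.

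**3. Distance between the cut-offs.** 153/120 = 1.275, and log10(1.275) = 0.1055.

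**4. Shift within one arm (assumed distributions).** If titres are log-normal with log10 standard deviation s, and a share p lies at or above 120, the share at or above 153 is Φ(z_p − 0.1055/s). Example: p = 0.75, s = 0.4 gives Φ(0.674 − 0.264) = Φ(0.411) = 65.9%.

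| s (assumed) | 50% becomes | 65% becomes | 75% becomes | 75% v 65% contrast becomes |
|---|---|---|---|---|
| 0.4 | 39.6% | 54.8% | 65.9% | 11.1 points |
| 0.6 | 43.0% | 58.3% | 69.1% | 10.8 points |
| 1.0 | 45.8% | 61.0% | 71.5% | 10.5 points |

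A single log-normal puts many values near the cut-off. With a well-separated mixture instead (half with median 20, half with median 800, s = 0.4, all assumed), the share falls from 50.3% to 48.9%, a shift of 1.4 points. Across these cases the shift runs from 1.4 to 10.4 points.

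**5. Shift in the contrast.** The last column applies the same model to the planned 75% v 65% with equal spread in both arms. Both arms move together, so the 10-point difference becomes 10.5-11.1 points. This is the share above the cut-off only, not the full response definition with its 4-fold route.

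**6. The response definition has two forms.** The Project Summary, the background section on seroconversion and immune response, and Special Assays or Procedures limit the 4-fold route to infants seropositive before vaccination. The endpoint text, the main Outcome measures/variables section and General analytical issues offer it as an alternative with no such limit. How reclassifying an infant at 120 to below 153 changes that infant's response status depends on which form is used, so the net effect on the primary response cannot be calculated from the documents.

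**The case against.** The strongest reply is that 153 already governs. The MBA section stands under an explicit statement of changes to the protocol, it is the only text with an MBA-specific limit, and the ELISA and PRNT sections tie 120 to neutralisation. On this view the remaining 120s are an edit not carried through. As a reading of intent this is persuasive, and it supports the choice of 153. It does not remove the contradiction, because the outcome and analysis sections name MBA and still print 120.

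Second, the primary response is not contradicted outright. General analytical issues attaches 120 to seroprotection, not to seroconversion, and an assay's analytical cut-off naturally supplies negative and positive. This stands: for seroconversion the fault is a missing explicit number, not two conflicting ones.

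Third, the earlier Bangladesh study cited under Special Assays or Procedures found baseline measles seroprotection at 9 months of only 0.42-1.25% by neutralisation. If the same holds here on MBA, very few Arm B infants could change baseline class. This also stands.

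The missing detection limit may be in the laboratory protocol that the MBA section refers to. That is possible, but the maternal classes should still be defined where objective 3 is analysed.

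A reader might infer that the cut-off was chosen after results were seen, since the assay changed after fieldwork ended. The documents do not support this: the DSMB section says all specimens are analysed after field activities are complete, so a change after fieldwork is not a change after results.

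**Conclusion.** Wrong as written. For seroprotection and the maternal class, the same MBA result is classed two ways in the current text. For the negative-to-positive part of the primary response, the MBA threshold has to be inferred.

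The firm effect is on the measles seroprotection proportions and the mothers' class: about 1 to 10 points within an arm, under distributions that are assumed because the documents give none. A reader might set that shift against the planned 10-point difference and conclude that the arm comparison is undermined. The documents do not support this. The shift is within an arm, and under the same log-normal model with equal spread the contrast moves by only about 0.5 to 1.1 points. A reader might also try to infer the direction of the effect on the primary response from antibody decay; that depends on which wording of the 4-fold route applies, which is itself unsettled.

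**What to change.** 1. Use ≥153 mIU/mL for every MBA-based measles seroprotection, baseline-seropositive and maternal classification: Project Summary, Special Assays or Procedures, main Outcome measures/variables, General analytical issues and Primary analytical approach. Correct the 1:120 notation in doing so. Keep 120 only for neutralisation results.
2. State in the MBA section that measles seroconversion by MBA means below 153 mIU/mL before vaccination and at or above 153 after. In the Project Summary, replace the undetectable condition with seronegative (<153 mIU/mL). Do not define undetectable as below 153: the decay model uses infants with maternal antibody detected at 6 months, and quantifiable values below 153 should stay in it.
3. Choose one response wording: the 4-fold route either limited to pre-vaccination seropositives or open to all, stated identically throughout.
4. For secondary objective 3, give the MBA lower quantification limit that defines the detectable class, or report two maternal classes as Special Assays or Procedures already does.
5. Report MBA at 120 as a labelled sensitivity analysis by arm.

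The cost is wording changes and one extra table. Reported seroprotection may be lower than at 120, and objective 3 may lose one maternal class. No new samples, visits or recruitment are needed.

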Our study hypothesis is that the proportion of children seroconverting after MR vaccine dose at 9 months following administration of an earlier MR vaccine dose at 6 months of age (Arm A) is not different compared with the immunogenicity obtained when MR vaccine dose is administered at 9 months to infants who have had no previous dose of MR vaccine (Arm B). A secondary hypothesis is the incidence and spectrum of adverse reactions following immunization will be similar between doses given at 6 and 9 months (Arm A), and at 9 months.

The following questions are to be answered by the study:

1. What is immunogenicity of MR vaccine at 6 months of age?
2. What is the impact of the 6-month MR dose on immunogenicity of the 9-month MR dose?
3. What are the frequency and severity of adverse reactions following MR vaccination at 6 months and 9 months?
4. What is correlation between the measles and rubella antibody levels in mothers and level of maternal antibodies in infants

Specific Objectives

Primary objectives

1. To assess immunogenicity of MR vaccine at 6 months of age
2. To assess immunogenicity of MR vaccine at 9 months of age among children without prior measles and rubella vaccination, compared with MR vaccine immunogenicity among those who had a prior MR vaccination at 6 months of age

Secondary objectives:

1. To assess the frequency of adverse reactions following administration of MR vaccine at 6 months
2. To compare the immunogenicity of the MR vaccine first dose administered at 6 months vs at 9 months.
3. To assess the proportion of mothers with undetectable, detectable and protective levels of measles and rubella antibodies

4. To determine the extent of variation in measles antibodies in a convenience sample of women of child bearing age in a population with a long standing measles vaccination program
5. To determine the extent of variation in rubella antibodies in a convenience sample of women of child bearing age in a population where rubella vaccine have been recently introduced
6. To determine if variation in antibody levels in infants at 6 months is predominately explained by variation in starting antibody levels in the mother in this population
7. To estimate the half-life of decay of measles and rubella antibodies in infants

Background

Measles

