Breastmilk does not give infants antibodies that protect against measles and rubella. Antibodies that are transferred through breastmilk are mostly IgA antibodies which mostly protect against gastrointestinal infections.

Response to early vaccination

Response to early measles vaccination, prior to 9 months of age, is affected by prematurity of the infant's immune system as well as neutralization of vaccine virus by circulating maternal antibodies. A number of studies have evaluated immunogenicity of early vaccination with single antigen measles vaccine. Studies conducted in the years after licensure of measles vaccine reported 60%-70% seroconversion with measles vaccine in infants <9 months of age. Additionally, some studies reported a suboptimal immune response to later vaccination in children who had been previously vaccinated at <1 year of age. Recently, in a study in children in California, USA, Gans et al reported no difference in cell-mediated immune response in children vaccinated at 6, 9 or 12 months (24). Gans et al. also reported that seroconversion in 6 month old infants was 77% among those who did not have maternal antibodies compared with 96% in those 12 months of age (24). Overall, while measures of humoral immunity (seroconversion and geometric mean titers) were lower in 6 month old infants compared with those 12 months of age, cell-mediated immunity responses in these two groups of infants did not differ. Significantly, early measles vaccination at 6 months of age was not associated with altered immune response to second dose of measles vaccine. A subsequent study of 55 infants by Gans et al confirmed the prior findings and reported an overall seroconversion of 86% in 6 month old infants. The only trial that evaluated the immunogenicity of early rubella vaccination was conducted in Brazil in 1990-91 and reported >90% seroconversion by 6 months of age in 24 infants (25).

Seroconversion and immune response

Seroconversion is defined as a change from an antibody seronegative to seropositive status after exposure to an antigen. Immune response definition includes seroconversion or a 4-fold or greater

increase in antibody titers among pre-vaccination seropositives, at 8 weeks after completion of vaccination series, after adjusting for decline in maternal antibodies.

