This study will be an open-label, randomized, 2-arm clinical trial. 620 children will be enrolled and randomized at 6 months of age to one of two study arms. The primary objectives of this study are to assess the immunogenicity of MR vaccine at 6 months, and assess equality of MR vaccine seroconversion administered at 9 months following administration of an earlier MR vaccine dose at 6 months of age compared with MR vaccine dose administered at 9 months only without previous MR vaccination. The study will enrol generally healthy 6 month old infants living in Matlab and who have never received an MR vaccine dose and have no history of measles or rubella. Participants will be followed to 11 months of age.

Infants in this study will be randomly assigned to one of two arms. Infants in Study Arm A will receive MR vaccine at 6 months of age (at enrolment) and at 9 months. Infants in Study arm B will receive MR vaccine only at 9 months.

Blood specimens will be collected from all infants at 6, 9 and 11 months of age. The 6 month sample is a pre-vaccination sample and mainly will be used to determine maternal antibody levels. For arm A, the sample collected at 9 months before the second MR dose will be used to assess antibody levels after the first MR dose at 6 months of age. For study Arm B, the 9 month sample will be used to assess measles and rubella antibody decay rate. The sample collected at 11 months will be used to assess immune response to either a two dose or a one dose schedule (arms A and B, respectively). The study design and participant evaluations are illustrated in the Table.

Table: Schematic representation of study arms

Arm		Age of participant				
		6 months	9 months	11 months	Sample size	Enrollment target (sample size + 10% attrition)
A	MR 6 & 9 months	MR •	MR •	•	279	310
B	MR 9 months	•	MR •	•	279	310
	Total (infants)				558	620
	Mothers	•			558	620

• Indicates blood collection
MR- Measles -rubella vaccination

Blood specimens will be collected from mothers of all enrolled infants at time of enrolment.

Study enrolment and withdrawal

A sample of 620 infants at age 6 months (180 days, +/- 7 days) of age (310 per each study arm) will be enrolled from population living in Matlab area. Inclusion and exclusion criteria are provided below.

Inclusion criteria: Infants

- Healthy infants at 6 months (180 days, +/- 7 days) of age (calendars will be provided to staff)

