Frozen sera will remain frozen during routine shipments to the laboratory at icddr,b and to the CDC measles/rubella laboratory in Atlanta. Shipment of serum will be made according to internationally recognized standards for transport of specimens.

Long-term specimen storage

The parents will be requested to permit storage of blood specimens for no more than 5 years for potential future use in studies. All specimens will be destroyed after 5 years from the end date of the study (the date of last study visit of the last participant to be enrolled). Specimens will be destroyed as per standard procedures of the laboratory for destruction of biohazardous waste.

Sample Size Calculation and Outcome (Primary and Secondary) Variable(s)

Sample size

The study will be powered to address the primary objectives. Sample size calculations are based on equality comparisons with 10% attrition.

Assuming 50% MR seroconversion to a dose at 6 months of age, a sample size of 271 per arm will provide a precision of +/-5% with a 0.90 probability of obtaining an estimate within the desired range. Adjusting for 10% attrition, the enrolment target is 302. Assuming a seroconversion for measles of 75% following a single dose given at 9 months of age, a seroconversion of 65% for a 9 month dose preceded by a 6 month dose, and power of 80%, a sample size of at least 279 per arm is required. Adjusting for 10% attrition, this sample size is inflated to 310. The overall study samples size will be 620 infants. 620 mothers of infants will also be enrolled. (Table)

Time to endpoint (and the corresponding objective)

Primary endpoint

- Time from randomization at 6 months to collection of blood at 9 months of age (To assess immunogenicity of MR vaccine at 6 months of age)
- Time from randomization to collection of blood at 11 months of age (To assess immunogenicity of MR vaccine at 9 months of age among children without prior measles and rubella vaccination, compared with MR vaccine immunogenicity among those who had a prior MR vaccination at 6 months of age)

Secondary endpoint

- Time from randomization 11 months (To assess the frequency of adverse reactions following administration of MR vaccine at 6 months)
- Time from randomization to 11 months of age (To compare the immunogenicity of the MR vaccine first dose administered at 6 months vs at 9 months)

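### Equal arms at 11 months would not show that the 9-month dose is unimpaired: the powered contrast compares a two-dose with a one-dose schedule, while study question 2 is about one dose

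*Combined protocol and SAP*

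**What the plan says.** All references are to the Combined protocol and SAP.

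- **The question.** Under Hypothesis to be tested, question 2 reads "What is the impact of the 6-month MR dose on immunogenicity of the 9-month MR dose". The hypothesis is that seroconversion after the 9-month dose is no different with or without a prior dose.
- **The measurement.** Study design: "The sample collected at 11 months will be used to assess immune response to either a two dose or a one dose schedule". The Secondary outcomes list describes the 11-month Arm A result as following a two-dose series. Primary analytical approach takes measles status before vaccination at 6 months in Arm A and at 9 months in Arm B.
- **The test.** A chi-square test across arms (end of Secondary analytical approach). No margin, alpha or sidedness is given.
- **The size.** The Sample size paragraph makes two calculations. Precision: "Assuming 50% MR seroconversion to a dose at 6 months of age, a sample size of 271 per arm". Comparison: "Assuming a seroconversion for measles of 75% following a single dose given at 9 months of age", then "a seroconversion of 65% for a 9 month dose preceded by a 6 month dose, and power of 80" per cent, leading to 279 per arm and 310 after attrition.

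The Sample size paragraph does not say whether the 65% is cumulative after both doses or belongs to the 9-month dose alone. The design and outcome sections favour the cumulative reading.

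**The concern.** An Arm A infant who converted after the 6-month dose and stays positive is a success at 11 months whatever the 9-month dose does. The contrast therefore adds the benefit of an extra dose to any effect of that dose on the next one, and the two can cancel.

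If they cancel, the test shows no difference, and the hypothesis as worded invites the conclusion that early vaccination leaves the routine dose intact. If the 9-month dose is unimpaired and the extra dose helps, the test can reject equality for a reason unrelated to interference. Whether early dosing blunts the routine dose is a main reason for the trial, and Response to early vaccination reports mixed evidence on it.

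**Working it through.** **1. The plan's own figures.** Inputs: 75%, 65%, 80% power, 1:1 allocation, 10% attrition. Alpha is not stated, so 5% one-sided and two-sided were both tried.

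n = [z_α√(2p̄(1−p̄)) + z_β√(p₁(1−p₁)+p₂(1−p₂))]² / d², with p̄ = 0.70 and d = 0.10.

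- One-sided 5%: (1.645 × 0.648 + 0.842 × 0.644)² / 0.01 ≈ 259. With continuity correction, (n/4)(1 + √(1 + 4/(nd)))² ≈ 278.3, so **279**. This matches. Two-sided 10% gives the same.
- Two-sided 5%: 329, or 349 corrected. No match.
- Attrition: 279/0.9 = 310. This matches.
- Precision: 1.645² × 0.25/0.05² = 270.6, so 271; 271/0.9 = 301.1, so 302. Both match.
- Power of 279 per arm for 75% vs 65%: 80.1% at z = 1.645 with correction. At two-sided 5%, (0.10 − 1.96 × 0.0388)/0.0386 = 0.62, so 73% (70% corrected).

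**2. What the 11-month proportion contains.** Let f be the first-dose response and q the response to the 9-month dose among first-dose non-responders. If first-dose responders stay positive, Arm A = f + (1−f)q.

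With f = 50%:

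- Equal arms: q = (0.75 − 0.50)/0.50 = 50%.
- Arm A at 65%: q = (0.65 − 0.50)/0.50 = 30%.

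**3. What an unimpaired dose would give.** This depends on how responses to the two doses are related, which the documents do not establish.

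- *Independent:* non-responders behave like unprimed infants, so q = 75% and Arm A = 0.50 + 0.50 × 0.75 = 87.5%. Equal arms are then a loss of 75 − 50 = 25 points, and 65% a loss of 45.
- *Nested:* all 6-month responders are among the 75% who would respond at 9 months. Then q = (0.75 − 0.50)/0.50 = 50% and Arm A = 75%. Equal arms mean no loss.

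Sensitivity to f (50% from the Sample size paragraph, 60–70% from Response to early vaccination):

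| f | Arm A if unimpaired, nested to independent | q at equal arms | q if Arm A = 65% |
|---|---|---|---|
| 50% | 75% to 87.5% | 50% | 30% |
| 60% | 75% to 90% | 37.5% | 12.5% |
| 65% | 75% to 91.25% | 29% | 0% |
| 70% | 75% to 92.5% | 17% | not possible unless first-dose responders are lost |

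**4. What the stated power covers (279 per arm, f = 50%, two-sided 5%).**

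- No impairment, independent: 87.5% vs 75%. Equality is rejected with 97% power, in favour of Arm A.
- 10-point impairment, independent (q = 65%): Arm A = 82.5%. Power is 58%, again in favour of Arm A. A one-sided test for a lower Arm A has power below 0.1%.
- 10-point impairment over the whole arm, nested: 65% vs 75%, the contrast that was powered.

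**5. What the 9-month sample can support.** At f = 50%, about 140 of 279 Arm A infants are below the cut-off before the 9-month dose. In Arm B it is about 276, taking off roughly 1% because Special Assays or Procedures cites baseline measles seroprotection of 0.42–1.25% at 9 months.

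- Power for 65% vs 75%: (0.10 − 1.96 × 0.0468)/0.0480 = 0.17, so 57% at two-sided 5%. At z = 1.645 it is 68%, or 64% corrected.
- Difference detectable with 80% power at two-sided 5%: about 13.5 points.

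**The case against.** **The 65% and the 50% do not contradict each other.** A reader might infer an arithmetic error. There is none: every stated size reproduces, the 65% is the alternative to be detected and not a forecast, and the 50% enters only the precision calculation, where it may be the maximum-variance choice. If the 65% belongs to the 9-month dose alone, the two figures describe different doses. This objection stands in full.

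**Equal arms need not mean a loss.** A reader might infer that 75% vs 75% proves a 25-point loss. That needs independent responses. The protocol names immune maturity and maternal antibody as determinants of response, and these could make the same infants fail twice. Under nesting, equal arms mean no loss. This also stands, but it supports the narrower point: the contrast cannot separate the two cases.

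**The denominator of about 140 is not fixed.** A reader might infer that the trial has 57% power for question 2. That figure needs strict seroconversion among infants below the cut-off, whereas the response definition also counts 4-fold rises in seropositives. It also changes alpha: at two-sided 5% the full 279 per arm gives only 73%. At the setting that reproduces 279, the like-for-like fall is from 80% to 64%.

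**The 60–70% range is a loose guide.** The text says studies "reported 60%-70% seroconversion with measles vaccine in infants <9 months of age", in a passage about single-antigen vaccine and early post-licensure work. It is not an MR rate at 6 months, so it serves here only as a sensitivity range.

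**The protocol already speaks of schedules.** Data Analysis describes a comparison of schedules, and 9-month pre-dose samples are taken in both arms. But no listed analysis uses the 9-month sample as Arm A's baseline for the second dose, and the hypothesis still refers to the dose.

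**Conclusion.** The concern holds as a mismatch between the planned contrast and the question it is meant to answer. The 11-month chi-square is a valid comparison of schedules. A result of no difference does not by itself show that the 6-month dose leaves the 9-month dose unimpaired.

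At 50% first-dose response, an unimpaired dose is compatible with Arm A anywhere from 75% to 87.5%, and equal arms with anything from no loss to a 25-point loss. The stated 80% is power for a 10-point difference between schedules, and only at one-sided 5% or two-sided 10% with continuity correction. It is also power for a 10-point impairment of the 9-month dose only under nesting.

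This rests on the cumulative reading of the 11-month outcome, on first-dose responders staying positive to 11 months, and on the plan's 50% and 75%. The documents do not show that the sample size is miscalculated or that the 9-month dose is expected to be impaired.

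**What to change.** Enrolment stays as it is.

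1. **Sample size paragraph.** Define the 65% as cumulative or dose-specific. State that the 80% power applies to the difference between schedules at 11 months, with the alpha and sidedness used.
2. **Data Analysis.** State that finding no difference between arms at 11 months will not by itself be taken to mean that the 6-month dose has no impact on the 9-month dose.
3. **Supportive analysis for question 2.** Use the 9-month pre-dose sample as baseline in both arms. Analyse seroconversion at 11 months among infants below the cut-off at 9 months, adjusted for the 6-month titre, and 4-fold rise among those above it. Report the seroconversion analysis with its expected n (about 140 vs 276 at 50% first-dose response), its detectable difference (about 13.5 points at 80% power, two-sided 5%), and the independent and nested bounds.

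The cost is wording and one analysis on samples already in the schedule. Special Assays or Procedures notes that field data collection is complete, so the change should be dated and labelled as made after that point.

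The subset is selected after randomisation. Its no-loss expectation in Arm A runs from 50% to 75%, a 25-point span that exceeds the 13.5 points it can detect. It can inform question 2 but cannot settle it alone.
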